Each subject will have OCT performed on each eye at baseline and then annually for 3 years (total of 4 OCT per subject). OCT will be performed on the Spectralis OCT system (Heidelberg Engineering, Germany) using the glaucoma protocol set. If the study center's available Spectralis OCT system has the neurology-oriented "N-site" software, then the RNFL scan (see below) will be obtained twice, once using the glaucoma protocol set and once using the axonal (N-site) protocol set. Pupillary dilation will not be routinely performed, as it is usually unnecessary for OCT (49). If dilation is deemed necessary to achieve adequate OCT quality (e.g., due to cataract), the subject may be excluded from the OCT portion of the study. Alternatively, dilation may be performed (with typical mydriatic eye drops) if the dilation and OCT are done after the other functional study assessments (e.g. EDSS, MSFC, LCVA, BRB-N) during the study visit, or if dilation/OCT are done on a separate visit day within a +/- 2 week window of other efficacy measures. In other words, pupillary dilation for OCT purposes will not be allowed to interfere with the other efficacy assessments that require vision for their performance.

Up to three different scans will be performed on each eye at each visit, to assess RNFL thickness, macular volume, and individual retinal layer thickness (ganglion cell layer, inner nuclear layer, etc). The RNFL scan will be obtained twice (once using the glaucoma protocol and once using the axonal protocol) if the axonal protocol is available. The axonal protocol (N-site) is optimized for detecting abnormalities in MS, and is thus the preferred method. However, all of the study sites are not expected to have access to the axonal protocol, while all will have the glaucoma protocol available. Therefore, we will obtain all scans on the glaucoma protocol (to ensure consistency of data), and acquire the axonal protocol RNFL scan as well when it is an option. The scans to be obtained are:

- i. **RNFL scan (circle scan)** – Standard settings for peripapillary RNFL with the Spectralis glaucoma protocol will be used: 12 degree (3.45 mm) circular scan manually centered on the optic disc, ART = 100, circle = 12°, 768 A-scans.
- ii. **Macular volume scan (posterior pole scan)** – The posterior pole scan from the glaucoma protocol set will be used, again using the standard settings: 30x25, 61 sections, 760 A-scans per section, distance between B-scans = 120 μ m, ART = 9.

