Multiple linear regression models will be used to test for between group differences in LCVA scores adjusted for other covariates. Binocular LCVA scores will be used to test for a treatment effect on vision changes; monocular LCVA scores will be used for correlation with OCT measures (from the matching eye). Generalized estimating equation (GEE) models will be used to test for between group differences in change over time in vision loss rates adjusted for other covariates. In addition correlation of LCVA with OCT measures (RNFL and macular volume) will be evaluated using Pearson correlation analysis (Spearman correlation will be used if measures have skewed distributions).

Between group differences in mean OCT macular volume scan measures will be tested using multiple linear regression models adjusted for covariates. mixed model analyses of repeated measures will be used to test for between group differences in change over time in OCT macular volume measures.

7. Study Procedures

A. Schedule of study procedures:

1. Symptoms questionnaire for subjective adverse events at baseline, 3, 6 and 12 months and then annually.
2. Comprehensive metabolic panel (CMP) and hemoglobin A1C (HbgA1C) at screening, 6 and 12 months, and then annually.
3. EDSS and DEXA scan (both hips/femurs and lumbar spine) at screening and then annually.
4. OCT at baseline and then annually.
5. MSFC, T25FW, 6MWT, LCVA, MSWS-12, AI, FSS and BRB-N at baseline and then annually.
6. Practice sessions (at screening visit:
 - a. BRB-N - 1 practice session

- b. PASAT - 2 practice sessions (in addition to the one administered during BRB-N)
- c. 9HP - 3 practice sessions

Table 1. Study Schedule

	V1 Screen 0 to -4 wks	V2 Baseline M0	V3 *** M3	V4 M6	V5 M12	V6 M18	V7 M24	V8 M30	V9 M36
Informed Consent	X								
Inclusion/Exclusion	X								
Injection Training		X							
Blood Pressure		X	X	X	X	X	X	X	X
Weight		X	X	X	X	X	X	X	X
Safety Lab Tests^a	X			X	X		X		X
Skin & Edema Assessment		X	X	X	X	X	X	X	X
OCT		X			X		X		X
LCVA		X			X		X		X
EDSS	X				X		X		X
Timed 25-Ft Walk		X			X		X		X
9-Hole Peg Test	XXX	X			X		X		X
PASAT (apart from BRB-N)	XX								
6 Minute Walk Test		X			X		X		X
MS Walking Scale - 12		X			X		X		X
Fatigue Severity Scale (FSS)		X			X		X		X
Hauser Ambulation Index		X			X		X		X
Brief Repeatable Battery	X	X			X		X		X
DEXA Scan^b	X ^c				X		X		X
Randomization		X							
Symptom Questionnaire		X	X	X	X	X	X	X	X
Concomitant Medications		X	X	X	X	X	X	X	X

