Subjects will be asked to contact their study site if they develop new symptoms that are concerning to them. The local study coordinator will record the reported symptoms on the Unsolicited AE Form, which will be reviewed by the local investigator. An unscheduled study visit will occur if the local investigator deems these AEs as potentially serious, possibly related to study medication, and/or requiring in-person assessment. If the reported symptoms are interpreted as mild and/or unrelated to study medication, the subject may be referred to their primary physician or advised to report back by phone with updates about symptom

evolution/resolution. Unscheduled visits will not be routinely performed for suspected MS relapse (see section 7D, Relapses), although they may occur in this situation if the reported symptoms are interpreted as a possible treatment-related AE. Assessments/procedures performed at an unscheduled visit will include all of the assessments done at Visit 3 (see Table 1) with the exception of study drug distribution; any further assessments and/or procedures (e.g. physical examination, other tests, referrals) will be done at the discretion of the local investigator.

F. Early Termination and Intent to Treat

Once subjects are randomized, regardless of if or the length of time they have been on blinded treatment, they will be included in the efficacy (intent to treat) analysis if efficacy data are available (that is, if they have completed at least one annual follow-up visit). Subjects who withdraw (e.g., due to side effects) prior to completing the Month 12 visit will be asked to return the study drug to the site, and to participate in annual phone calls (Months 12 and 24), and to return to the site for the final visit at Month 36. Subjects who withdraw after completing the Month 12 visit will be asked to return the study drug to the site, and to complete the remaining annual study visits (i.e., Month 24 and Month 36) even though they are not receiving drug. Subjects are of course allowed to decline further participation, in which case they would be considered lost-to-follow-up.

G. Data Safety Monitoring

A DSMB will be formed and will consist of one MS specialist, one neurologist familiar with the evaluation and treatment of MS but not otherwise associated with the study, and the study biostatistician. A DSMB chairperson will be chosen from one of the two neurologists on the DMSB.

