Safety data will be reviewed by the DSMB at 6 and 12 months and then annually, starting from the time the first subject receives a dose of study medication and ending at participant study completion (i.e., no active participants on study drug and enrollment closed). Reports from all DSMB meetings will be forwarded to the Institutional Review Board (IRB). Any SAEs or unexpected AE's reported at other times will be reviewed by the head of the DSMB and reported to other members of the DSMB if considered significant enough to warrant interim review by the full committee. In the event of unanticipated SAEs that reflect new or increased risk to the subjects and are considered possibly related to the study medication or procedures (UPIRTSO) the funding sponsor and all study sites will be notified within 48 hours of the local investigator learning of the event. The local IRB will be notified within that IRB's policy timelines (e.g., the University of Minnesota IRB will be notified within 10 business days). A detailed analysis of all AEs will be conducted at the end of the first year of the study. The efficacy measures will also be analyzed annually throughout the study to see whether any signal of benefit is appearing. However, the study will be terminated only if there are unacceptable adverse events, not because of lack of any efficacy signals since it may take the entire 3 year duration of the study for any

beneficial effect to become manifest. Study termination due to safety concerns will be at the discretion of the DSMB; no pre-specified stopping rules will be used.

8. Cytokine sub-study

There are multiple mechanisms by which melanocortins such as adrenocorticotrophic hormone (ACTH) might alter the course of multiple sclerosis (MS) in a beneficial way (16, 54). One such mechanism is altering the balance between pro-inflammatory and anti-inflammatory cytokines via direct immunomodulating effects of melanocortins on immune system cells. A sub-study will be performed (at the University of Minnesota site only) to evaluate the change in plasma cytokine levels in subjects receiving ACTH compared to those receiving placebo, in order to better elucidate the possible mechanisms of ACTH in MS.

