Subjects enrolling in the main study at the University of Minnesota site will be invited to participate in the plasma cytokine sub-study as well. Subjects who enroll in the sub-study will, at the annual study visits when they have blood drawn for safety blood tests, have additional blood tubes drawn for the cytokine analysis (2 EDTA tubes). Tubes will be mixed, centrifuged, and then plasma aliquoted and stored at -80° C. Leukocytes (buffy coat) will also be aliquoted and mixed with *RNAlater* (a reagent that stabilizes RNA for future possible analysis of gene expression) and stored at -80° C. Leukocytes or whole blood samples will also be stored for possible future DNA analysis. The potential future RNA and DNA analyses are not currently planned as part of the sub-study, and subjects may opt out of this aspect (i.e. choose not to have genetic material stored) in the consent form.

Cytokine levels will be assessed with multiplex cytokine assays on the Luminex system, and will be performed by the Cytokine Reference Laboratory at the University of Minnesota. Approximately 25-30 analytes (cytokines, chemokines, growth factors, etc) will be measured. The current list of analytes planned for the study include: Eotaxin, FGF-2, G-CSF, GM-CSF, IFNa2, IFNg, IL-1b, IL-1ra, IL-2, IL-4, IL-5, IL-6, IL-7, IL-8, IL-9, IL-10, IL-12(p70), IL-13, IL-15, IL-17, IP-10, MCP-1, MIP-1a,b, TNFa, VEGF, M-CSF, and MIG. Assays will be performed in batches of 40 samples (in duplicate) at a time; thus each "batch" would correspond to 10 subjects worth of samples (10 subjects x 4 samples/subjects = 40 samples). We anticipate the total number of subjects to be enrolled in the sub-study to be between 30 and 80. Differences between the active (ACTH) and placebo groups for plasma levels of each analyte will be assessed with multiple linear regression models adjusted for covariates (e.g. age, gender, MS phenotype) and/or mixed model analyses of repeated measures.

9. References

1. J. Frischer *et al.*, The relation between inflammation and neurodegeneration in multiple sclerosis brains. *Brain*. **132**, 1175-1189 (2009).
2. C. Stadelmann, C. Wegner, W. Bruck, Inflammation, demyelination, and degeneration - recent insights from MS pathology. *Biochim. Biophys. Acta*. **1812**, 275-282 (2011).
3. W. Bruck, C. Stadelmann, Inflammation and degeneration in multiple sclerosis. *Neurological Sciences*. **24 Suppl 5**, S265-S267 (2003).

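### Section 8's cytokine collection rule, read literally, gives three on-treatment samples per subject, while its assay plan counts four and its aim is change; the pre-treatment draw is not named anywhere

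*Combined protocol and SAP*

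**What the plan says.** The sub-study in section 8 runs at one site and is meant "to evaluate the change in plasma cytokine levels in subjects receiving ACTH compared to those receiving placebo". Sub-study subjects will, "at the annual study visits when they have blood drawn for safety blood tests, have additional blood tubes drawn for the cytokine analysis". Later in the section, assay batches are sized on "10 subjects x 4 samples/subjects = 40 samples". Expected enrolment is given as "We anticipate the total number of subjects to be enrolled in the sub-study to be between 30 and 80". Arms are to be compared on the plasma level of each analyte using "multiple linear regression models adjusted for covariates (e.g. age, gender, MS phenotype) and/or mixed model analyses of repeated measures".

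The safety blood schedule is in section 7.A, item 2: "Comprehensive metabolic panel (CMP) and hemoglobin A1C (HbgA1C) at screening, 6 and 12 months, and then annually". Table 1 agrees. It marks safety labs at V1 (Screening), M6, M12, M24 and M36, and none at V2 (Baseline). Table 1 has no cytokine row.

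Two other places show how the plan uses the word *annual*. Section 7.F asks subjects who withdraw after Month 12 to "complete the remaining annual study visits (i.e., Month 24 and Month 36"). Section 5.G schedules OCT "at baseline and then annually for 3 years (total of 4 OCT per subject"), so baseline is named separately from the yearly visits.

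**The concern.** The collection rule sets two conditions: the visit is annual, and safety blood is taken at it. With the plan's own use of *annual*, the visits that meet both all fall after treatment has started. This conflicts with the four samples per subject in the same section, and it fits poorly with an aim stated as change.

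A pre-treatment sample cannot be recovered once the first pulse has been given. A coordinator working from the text would have no instruction to draw one. Change from pre-treatment could then not be computed, and arms of perhaps 15 to 40 subjects could not be adjusted for the analyte's own starting level.

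**Working it through.** **Inputs.** Collection rule, batch arithmetic, sub-study size and model: section 8. Safety blood visits: section 7.A item 2 and Table 1. Meaning of *annual*: sections 7.F and 5.G. Allocation 1:1: section 6.C.

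**1. The plan's own figure.** 10 subjects × 4 samples = 40 per batch. The product is right; the question is whether the 4 follows from the rule.

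**2. Count from the rule.**
- Annual visits: {M12, M24, M36}.
- Safety blood visits: {Screening, M6, M12, M24, M36}.
- Visits in both sets: {M12, M24, M36}, so 3 per subject, of which 0 are pre-treatment.
- Per 10 subjects: 10 × 3 = 30, not 40. A 40-sample batch would hold 40/3 = 13.3 subjects.
- Totals: 30 × 3 = 90 rather than 30 × 4 = 120 for 30 subjects; 80 × 3 = 240 rather than 80 × 4 = 320 for 80 subjects.

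**3. Which visit sets give four?**
- Screening + M12 + M24 + M36 = 4, one pre-treatment. Screening is not an annual visit.
- M6 + M12 + M24 + M36 = 4, none pre-treatment. Month 6 is not an annual visit.
- M0 + M12 + M24 + M36 = 4, one pre-treatment. This needs *annual* to include month 0 and safety blood to be drawn then, which happens only if Screening and Baseline are combined. Section 5.C allows for that case.
- All safety blood visits = 5.

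Every set of four departs from the literal rule or applies only to some subjects.

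**4. What three on-treatment samples support.** They support a randomised comparison of levels at Months 12, 24 and 36, adjusted for age, gender and MS phenotype, and a comparison of change from Month 12 onward. They do not support change from pre-treatment or adjustment for the starting analyte level.

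**5. Possible effect on precision.** The documents give no cytokine effect size, correlation or power target, so this step is illustrative. Assumptions: a difference of 0.5 SD at every visit, analysis of the mean of the three annual samples, the same correlation r between any two samples from a subject, two-sided 5% test, 25 per arm (within the 15 to 40 per arm implied by 30 to 80 subjects).
- Variance without a pre-treatment sample, in SD² units: V0 = (1 + 2r)/3.
- Residual variance with it as a covariate: V1 = (1 + 2r)/3 − r².
- Noncentrality: (0.5/√V) × √(n/2), used in a noncentral t with 2n − 2 degrees of freedom, one fewer with the covariate.
- Example at r = 0.5: V0 = 2/3 = 0.667 and V1 = 0.667 − 0.25 = 0.417.

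| r | V0 | V1 | Power without | Power with | Gain (points) |
|---|---|---|---|---|---|
| 0.1 | 0.400 | 0.390 | 78% | 79% | 1 |
| 0.3 | 0.533 | 0.443 | 66% | 74% | 8 |
| 0.5 | 0.667 | 0.417 | 56% | 76% | 20 |
| 0.7 | 0.800 | 0.310 | 49% | 87% | 38 |
| 0.8 | 0.867 | 0.227 | 46% | 95% | 49 |

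At r = 0.7 the corresponding figures are 32% and 66% with 15 per arm, and 69% and 98% with 40 per arm. The gain arises only if the pre-treatment level is in the model; the example covariates in section 8 do not list it.

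**The case against.** The best answer is that the plan shows its own intent. Four samples, an aim of change, the parallel OCT schedule of baseline plus three yearly measurements, and an existing screening blood draw all point to one pre-treatment sample and three annual ones. The rival set of four that uses Month 6 breaks the annual condition. The sub-study runs only at the primary study site, so sites cannot diverge in how they read it. Where Screening and Baseline are combined, safety blood would be taken at that visit before treatment, and a reader who counts month 0 as annual would then get the fourth sample.

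Most of this stands as evidence of intent, and it makes a wording omission the likeliest explanation. It does not supply the missing instruction. The combined visit is optional and covers only some subjects, section 7.F uses *annual* for post-baseline visits, and Table 1 has no row to settle the matter.

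Some stronger readings go too far:
- A reader might infer that the sub-study cannot measure change at all. It can compare on-treatment levels and change from Month 12 onward, and section 8's stated analysis compares levels.
- A reader might infer that chance imbalance cannot be corrected. Age, gender and phenotype are still adjusted for; only imbalance in the analyte's own starting level is beyond reach.
- A reader might infer a large loss of power. That holds only if r is moderate or high, and the documents give no value.

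**Conclusion.** The inconsistency is real and should be corrected. Read literally, the rule gives three samples per subject and none before treatment, against the four per subject (30 against 40 per 10 subjects) on which the assay plan is built. This count rests only on the plan's text and needs no outside assumption.

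What would be lost is change from pre-treatment and adjustment for the starting analyte level. The loss of precision could be negligible or large: about 1 to 49 percentage points of power across r = 0.1 to 0.8, under an assumed constant 0.5 SD effect, equal correlation and 25 per arm. The documents do not show that a baseline sample was meant to be left out; the count of four suggests the opposite. The sub-study is single-site and exploratory, so the primary endpoint, the trial's sample size and the main analyses are unaffected.

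**What to change.** - In section 8, replace the collection sentence with wording such as: *Cytokine tubes are drawn before the first dose of study drug (with the Screening safety blood, or at Baseline before the first injection) and at Months 12, 24 and 36.*
- Add a cytokine row to Table 1 showing those visits.
- State that sub-study consent is obtained before that first draw.
- Add the pre-treatment analyte level as a covariate in the cytokine models.

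Four samples per subject and 40 per batch then hold: 120 samples (3 batches) for 30 subjects and 320 (8 batches) for 80.

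The cost is small: a few sentences and one table row. The assay plan already counts four samples, and a screening blood draw already exists. Tubes taken at Screening are wasted for subjects who fail screening. Drawing at a separate Baseline visit avoids that but adds a blood draw where none is now scheduled.
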